## Processing:

- 1) Stool. Samples will be processed by members of PI [name] lab listed in this protocol.
- 2) Blood. Samples will be processed by Dr.[name]'s laboratory.
- Storage: All samples will be stored in locked -80°C freezers in laboratories in Lipman Hall ([name]) and New Jersey Institute for Food, Nutrition and Health ([name]) of Rutgers University until analysis. Samples will only be accessible by authorized research personnel named in this protocol. Specimens will be stored until they are no longer in a fit state for scientific analyses.
- **Disposition**: When specimens are no longer in a fit state for scientific analyses, they will be destroyed by incineration by authorized research personnel named in this protocol.
- B. Secondary Specimen Collection Not applicable.

## 1.9 Data Collection

## A. Primary Data Collection

## Location:

- Participants will be interviewed with Appetite and physical activity questionnaires and diet 24-hour recall at the clinical room at IFNH building.
- o fMRI will be conducted at the CAHBIR ([name]).
- Lab draws will be performed at IFNH or CAHBIR

## Process of Data Collection:

- Study coordinators will interview participants with questions in the appetite and physical activity questionnaires and for 24-hour recall.
- fMRI Session: Participants will complete an online MRI safety screening form prior to the study day (Appendix E). The form must be reviewed by the certified MRI Technologist prior to entry into the scanner room. The individual will be positioned in the magnet and will receive an anatomical scan followed by resting state and food picture fMRI scans. They will then be taken out of the scanner, consume a meal and then have a brief anatomical scan for purposes of alignment with their high-resolution MRI and a repeat of their fMRI scans.
- Timing and Frequency: The interviews and scanning will be conducted at Week 0 and Week 4.
- Procedures for Audio/Visual Recording: N/A

## Study Instruments:

- See Appendix C for the appetite questionnaire
- See Appendix G for the physical activity questionnaire
- MyFitnessPal application will be used to calculate caloric intake from 24-h diet recall

## Ethnographic Studies, Interviews, Or Observation: N/A

Subject Identifiers: participants' names and birthday will be linked with the data collected.

## B. Secondary Data Collection

NA

- Type of Records: NA
- Location: NA
- Inclusion/Exclusion: NA
- Data Abstraction Form(s): NA

## 1.10 Timetable/Schedule of Events

We expect to complete this trial within one year upon institutional approval. Detailed timeline is as follows:

	Preparations	M1	M2	M3	M4	M5	M6	M7	M8	M9	M10	M11	M12
Institutional approval, staff training and material development Recruitment													
Intervention, sample measurement and clinical data collection													
Bioinformatics and data analysis													
Results dissemination													

#### 2.2 Research Staff Training

All investigators have successfully completed the Collaborative Institutional Training Initiative (CITI) training.

#### 2.3 Other Resources

Gut microbiome analysis will be performed at the Microbiome Core of the New Jersey Institute for Food, Nutrition and Health of Rutgers University. The Core owns a next-generation sequencing platform (Ion GeneStudio S5, ThermoFisher Scientific) to perform 16S rRNA gene sequencing and a 2X Intel Xeon Skylake 6130 Node (22M Cache, 2.666 MHz, 192 GB RAM, 5 TB storage) of the high-performance computing cluster Amarel at Rutgers University for statistical analyses and bioinformatics. fMRI will be performed at CAHBIR of the Robert Wood Johnson Medical Center. The proposed study will have access to a state-of-the art Siemens 3T MRI scanner which allows for high resolution multi-band collection optimized for imaging regions in ventral brain regions involved in feeding. The image processing facilities at CAHBIR is connected to Rutgers' high-performance computing facilities to allow rapid parallel processing of imaging data.

#### 3.0 Multi-Center Research

Not applicable

## 4.0 Subject Considerations

## 4.1 Subject Selection and Enrollment Considerations

#### A. Recruitment Details

Patients with the diagnosis of PWS and/or hyperphagia will be recruited from [name] pediatric endocrinology RWJMS clinic and DEEP6 software.

## B. Subject Screening

## Inclusion Criteria

- Aged between 18-45 (inclusive)
- Confirmed PWS with genetic testing or documented ICD9/10 coding for hyperphagia
- No growth hormone treatment in the previous 6 months
- Body weight < 300 lbs.
- Exclusion Criteria
  - History of other gastrointestinal disorders such as small intestinal bacterial overgrowth, celiac disease, inflammatory bowel disease, or irritable bowel syndrome.
  - Pregnancy or breastfeeding
  - Prior gastrointestinal or bariatric surgery
  - Immunocompromised e.g., cancer treatment, bone marrow/organ transplant, immune deficiency, poorly controlled HIV/AIDS, prolonged use of steroids or other immunosuppressant medications
  - Antibiotic administration in the previous 30 days
  - o Administration of pre/probiotic supplements or antibiotics.
  - Growth hormone administration in the previous 6 months
  - Have access to a smartphone, tablet, computer, or other qualifying internet-enabled device and be able to follow instructions.

HRP-503a - TEMPLATE - Interventional Research Protocol 1.1.21 Protocol Title: Gut microbiota and hyperphagia in PWS Protocol Version Date: October 7, 2022

- o Individuals who are not proficient in English
- Contraindications for MRI scanning, including Ferrous material implanted in or on the 0 body, including flakes or filings, surgical clips, bullets, or electrical devices such as a pacemaker, or nonremovable ferrous jewelry (fillings in teeth and permanent retainers are permitted). Individuals with surgical pins or plates above the neck are excluded. Surgical pins or plates below the neck are exclusions, except when the material is fixed to bone, and considered acceptable by the Reference Manual for Magnetic Resonance Safety. Implants and Devices, 2020 Edition. Almost all recent orthopedic implants are made of materials that are not ferromagnetic and therefore are safe for scanning, and even though some screws are still made of ferromagnetic materials these are firmly screwed into bone. In cases where the material is unknown or deemed unsafe for scanning by the Reference Manual for Magnetic Resonance Safety. Implants and Devices, the participant will be excluded. History of eye injury involving metallic materials, shavings in eyes, or welding without a face mask. Lead/iron tattoos and tattoos performed by a nonprofessional artist if the pigment material is unknown. Claustrophobia (history of significant anxiety in closed places). Back problem that would prevent the subject from laying still comfortably for up to 60 minutes.

## C. Privacy Protections

Should any participants desire not to interact with or provide personal information to specific members of the research team, they may report such a need to the PI and the arrangement of the research personnel will be adjusted accordingly. Participants will not be required to provide a reason if they desire not to do so. If changing the research personnel is not possible, the PI will discuss with the subjects about alternative solutions.

Each participant will be assigned a unique identification code. A master code identifier which links the identification code and personal information will be maintained separately from the study data. Subject information is only accessible to named investigators in this protocol and authorized research personnel. All data and materials collected during this study are for research purposes only, and the data will be kept in strict confidence. De-identified information and biospecimens collected for this research may be used by or distributed to investigators for other research without obtaining additional informed consent from you.

Individuals must include their name on the MRI screening form, which includes private health information. This form is only visible to the study staff and the MRI technologist.

## 4.2 Obtaining Identifiable Information About Non-Subjects

Not applicable

## 4.3 Number of Subjects

A. Total Number of Subjects

10 patients; 5 male and 5 female

- B. Total Number of Subjects If Multicenter Study N/A
- C. Feasibility

DEEP6 identified 26 patients via EPIC system who had the diagnosis of PWS with only 5 patients meeting our inclusion criteria. For this reason we are expanding our diagnosis coding to include hyperphagia syndrome. Given hyperphagia is a hallmark feature of PWS and the particular behavior we are aiming to study, this expansion should improve our subject pool and allow us to enroll 10 patients.

## **4.4 Consent Procedures**

#### A. Consent Process

#### Location of Consent Process

The electronic consent process will take place during virtual interviews on Rutgers Zoom, a HIPPA compliant platform. Individuals who are willing to participate in this study will provide their electronic informed consent along with their guardians on DocuSign, a HIPPA compliant platform during the interview.

Ongoing Consent
 Not applicable

## Individual Roles for Researchers Involved in Consent

Study coordinators will conduct a consent interview to explain all aspects of the study and answer any questions the prospective participants may have.

 Consent Discussion Duration The consent discussion will take approximately 30 min.

## Coercion or Undue Influence

In order to minimize the possibility of coercion or undue influence, the consent process will not be conducted by research personnel who have any known relationship or conflict of interest with the prospective participants.

#### Subject Understanding

Throughout the consent process the prospective participants will be encouraged to ask any questions should they feel the need to do so. The consent process will be divided into a series of small sections. Members of the research team will summarize each section, use probe questions to check for sufficient understanding before proceeding to the next section.

## Protecting Privacy

Should any participants desire not to interact with or provide personal information to specific members of the research team, they may report such a need to the PI and the arrangement of the research personnel will be adjusted accordingly. Participants will not be required to provide a reason if they desire not to do so. Should changing of the research personnel is not possible, the PI will discuss with the subjects about alternative solutions.

Each participant will be assigned a unique identification code. A master code identifier which links the identification code and personal information will be maintained separately from the study data. Subject information and de-identified study data are only accessible to named investigators in this protocol and authorized research personnel. All data and materials collected during this study are for research purpose only, and the data will be kept in strict confidence. No information will be given to anyone without permission from the subjects. Should an incidental finding appear on the subject's MRI, the MRI will be shared with a neuroradiologist from University Radiology Group. No name will appear on the MRI to protect the participant's privacy.

## B. Waiver or Alteration of Consent Process

## Waiver or Alteration Details

We are requesting an alteration of the consent process. Prospective participants will be provided with a copy of the consent form prior to a virtual consent interview. During this interview, the study coordinator will go through the contents of the consent form with the all

applicable parties (subject, surrogate, witness, and research team member) will provide signatures on the consent form if the prospective participants are willing to provide information for eligibility screening. This is being done to minimize in-person contact during the pandemic. The alteration refers to the utilization of virtual consent.

## Destruction of Identifiers

The master code identifier, which contains personal information of subjects and the participant code assigned to them, will be deleted from the server 6 years after study completion.

 Use of Deception/Concealment Not applicable

## C. Documentation of Consent

## Documenting Consent

Prospective participants and the study coordinator who conducts the consent process will view and provide electronic signatures on the consent form in real-time through DocuSign, and both parties will keep a copy of the form.

 Waiver of Documentation of Consent (i.e., will not obtain subject's signature) Not applicable

## 4.5 Special Consent Populations

- A. Enrolling Minors-Subjects Who Are Not Yet Adults N/A
- B. Enrolling Wards of the State N/A
- C. Enrolling Non-English-Speaking Subjects N/A
- D. Enrolling Adults Lacking Decision-Making Capacity (Surrogate Consent) Given the nature of PWS, all patients will lack decision-making capacity and require surrogate consent.

Subjects will be assessed by [name], not affiliated with the study team. He will assess if they are able to understand the details of the research and if she/he can make a decision about taking part in the study. He will document this determination in the electronic medical record. If the answer is yes, consent will be obtained by the individual.

If the subject does not have capacity to make informed decisions, [name] will be notified and will obtain their Advance Directive from the patient or surrogate who has accompanied them to their clinic visit. If the advanced directive exists and indicates that the potential subject would not want to take part in proposed medical research, the subject will not be considered for the study. If the advanced directive does not exist or does not indicate that the subject would object to taking part of proposed medical research, The determination of consent will be provided to the patient and a surrogate.

Surrogate will be chosen from the highest category of surrogate decision-making priority. The surrogate will be contacted by phone. If one or two or more available persons in the same order of priority expresses opposition to the participation of the subject in the study, the investigator must exclude the subject from the study. If two or more available persons are in different orders of priority, refusal to consent by a potential surrogate who is of higher priority controls and will not be superseded by the consent of a person who is of a lower priority.

HRP-503a - TEMPLATE - Interventional Research Protocol 1.1.21 Protocol Title: Gut microbiota and hyperphagia in PWS Protocol Version Date: October 7, 2022

Once identified, the research staff in Rutgers will contact the surrogate via a phone call to provide an overview of the study, requirements for research participation, and review eligibility for the study (Appendix A). If the surrogate provides assent to participation and candidates are eligible for the study, a virtual informed consent interview with the research team will be scheduled (Appendix B). Subjects who are able to understand the concept of participating in a particular study will be asked to assent to the study; those that are unable to understand the concept of participating in a particular study will not be asked to assent. For studies at RWJUH, the Chaplain is the designated witness for studies utilizing surrogate consent.

If subject express dissent to participation or if a surrogate withdraws consent, subject will be withdrawn from the study. No further testing will take place and high-fiber supplement will be stopped.

# E. Special Consent Considerations N/A

## 4.6 Economic Burden and/or Compensation for Subjects

## A. Expenses

We do not expect any expenses the participants will incur by taking part in the research. The compensation should cover travel costs.

## B. Compensation/Incentives

Compensation will be awarded via ClinCards. Participants will receive compensation for the following milestones:

- \$25.00 after the completion of sample collection and shipment at Day 0
- \$25.00 after the completion of sample collection and shipment at Day 28
- \$30.00 after the completion of questionnaire at Day 0
- \$30.00 after the completion of questionnaire at Day 28
- \$50.00 after the completion of fMRI examination at Day 0
- \$50.00 after the completion of fMRI examination at Day 28
- \$50.00 after the completion of blood draw at Day 0
- \$50.00 after the completion of blood draw at Day 28

## **C** Compensation Documentation

Compensation will be awarded via ClinCards. Compensation will be tracked utilizing an excel sheet, which will also be stored in an encrypted, password-protected file.

## 4.7 Risks of Harm/Potential for Benefits to Subjects

## A. Description of Risks of Harm to Subjects

Reasonably Foreseeable Risks of Harm

Measuring fasting blood glucose during the study both involves a finger prick that pierces the skin. There may be a bruise, bleeding, or infection, at the place where the skin is pierced. However, infection is rare. Collecting fecal samples at home may impose inconvenience for the participants and their families. Participants taking NBT-BN108 may experience gastrointestinal symptoms (e.g. abdominal pain/discomfort, constipation, or bloating). These discomforts are

minor and should not last longer than a few hours. This product is low in digestible and simple carbohydrates and may reduce food intake.

There are no known health risks associated with the magnetic field produced by this 3.0T scanner in healthy adults. The FDA has indicated that they consider MR imaging on machines up to 4.0T to pose no risk (https://www.fda.gov/medical-devices/cdrh-research-programs/magnetic-resonance-imaging-mri-safety-and-effectiveness). Sammet (2016) provides discussion of MRI safety issues, each of which can be avoided with proper management. These include:1) attractive forces and torque caused by the magnet, 2) thermal effects caused by the radiofrequency fields, 3) peripheral nerve stimulation due to switching gradients, 4) hearing damage caused by the acoustic noise of the gradient system, 5) questions of risk for a fetus, 6) claustrophobia and other discomforts. These are briefly detailed below.

*Attractive Forces*: Ferrous material can be pulled toward the magnet, causing injury to a subject. These forces can cause metallic implants to be attracted to the magnet. The magnet can erase credit cards and other types of swipe cards.

Thermal Effects: The radiofrequency field can cause heating of ferrous material that are in the field, this is a concern for metal implants, and tattoos on the skin that specifically contain metal (iron).

Peripheral Nerve Stimulation (PNS): Although none of the planned scans involve parameters that should cause any peripheral nerve stimulation (tingling sensation caused by stimulation of a sensory nerve or motor twitch caused by stimulation of a motor nerve), it is hypothetically possible for this to occur in a scan in which magnetic gradients are being rapidly switched because the gradient cause a neuron near the surface of the skin or muscle to "fire". While the gradient performance of the magnet is not expected to produce PNS within the operational limits defined by Siemens, they remain a possibility for a small minority of sequences. Note that PNS is not considered an adverse event because when it occurs, it is an issue only of patient comfort rather than a safety concern.

Hearing damage: The gradient system noise often reaches 100dB. Sustained exposure to this volume of noise without noise reduction devices can cause hearing damage. *Claustrophobia, and* 

Additional Discomforts: Some participants experience anxiety due to the enclosed nature of the space in the scanner and head coil. Some potential minor discomforts associated with the procedures include back discomfort from lying in one position.

Incidental Findings: An incidental finding could arise during scanning. Learning of an incidental finding could cause psychological distress.

• Risk of Harm from an Intervention on a Subject with an Existing Condition

Although 3.0 T MRI is safe for healthy individuals several existing conditions, or situations can increase risk, or can increase the risk of discomfort. Persons at primary risk from exposure to the magnet include persons with metal surgical implants, and anyone with implanted electric/magnetic devices (e.g. a pacemaker, aneurism clips, IUDs). Such individuals are therefore excluded from the study.

- Other Foreseeable Risks of Harm N/A
- Observation and Sensitive Information N/A

HRP-503a - TEMPLATE - Interventional Research Protocol 1.1.21 Protocol Title: Gut microbiota and hyperphagia in PWS Protocol Version Date: October 7, 2022

B. Procedures which Risk Harm to Embryo, Fetus, and/or Pregnant Subjects N/A

## C. Risks of Harm to Non-Subjects

Fecal sample collection at home may impose inconvenience for individuals in the same household.

D. Assessment of Social Behavior Considerations N/A

## E. Minimizing Risks of Harm

Participants will be provided with oral and written instructions and supplies to collect fecal samples at home without direct physical contact with the specimens throughout the process (Appendix D). The specimens will be stored in a sealed container, a leak-proof secondary package (a sealable plastic bag lined with absorbent pads) and an outer package (e.g. a shipping box). Participants are not required to store the samples at home; they will mail the specimens to the research team using the shipping supplies provided.

To minimize adverse effects due to NBT-NM108, they will also be advised to drink enough fluids throughout the study (approximately eight 8-ounce glasses of fluid a day including the amount of water taken together with NBT-NM108) to avoid constipation. Participants will be asked to monitor potential adverse events daily. If participants report an adverse event, a member of the study team will contact them to ask follow-up questions about the degree of severity (mild, moderate, or severe) and the frequency of the adverse events. The study physician (PI [name]) will assess the adverse events and, if necessary, she will instruct the participants to discontinue treatment.

Measuring fasting blood glucose during the study both involves a finger prick that pierces the skin. There may be a bruise, bleeding, or infection, at the place where the skin is pierced. However, infection is rare. To minimize adverse effects, venipuncture will be done by a certified venupuncturist.

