## A. Schedule and Administration

Participants will receive NBT-NM108 prepared as muffin (each contains 30 g of the product) for 4 weeks. The dosage will be 2 muffins a day. This dosage of NBT-NM108 will provide 24 g/day of dietary fibers of diverse physicochemical structures as sources of fermentable carbohydrates for the gut microbiota. Participants will be given a supplement diary to keep track of consumption of muffins along with potential side effects (**Appendix H**).

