## Hospitalization during study

If patients are hospitalized during the study, they will be removed from the study and discontinue all data and sample collection. Subjects will need to contact the study PI, [name], D.O. at [name] if hospitalized during the study.

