## 6.3 Data and Safety Monitoring

## A. Data/Safety Monitoring Plan

A Data and Safety Monitoring Board (DSMB) will approve the protocol before the study is initiated, and after 30% of the participants complete 14 days of the intervention to review study progress including recruitment, retention, adherence, adverse events and study outcomes, as well as to ensure that participant safety is addressed adequately. Reports of adverse events will be used to assess the safety of the study.

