## B. Data/Safety Monitoring Board Details

The DSMB will include Rutgers University faculty members with expertise in medicine, epidemiology and/or statistics who are not directly involved with the study. The Board will meet before the study is initiated, and after 30% of the participants complete 14 days of the intervention to review study progress and provide recommendations related to continuing, modifying or terminating the study. Any serious adverse event that is life-threatening or results in death, that is possibly, probably, or related to the research protocol, will trigger an immediate suspension of the research. All details about the DSMB are found in **Appendix F.** 

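### For participants enrolled by surrogate consent, the available text names only the participant as a source of adverse-event information between Week 0 and Week 4

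*Combined protocol and SAP*

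**What the plan says.** Four places describe how harms become known and acted on.

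- **Reporting (4.7 E, Minimizing Risks of Harm).** "Participants will be asked to monitor potential adverse events daily. If participants report an adverse event", staff then get in touch. The contact covers severity and frequency. The study physician then assesses the event and, if necessary, "she will instruct the participants to discontinue treatment".
- **Diary (1.7 A).** "Participants will be given a supplement diary to keep track of consumption of muffins along with potential side effects". The text does not say who else may complete it, or when it is collected or read.
- **Hospitalisation (Hospitalization during study, under 4.7).** A hospitalised patient is removed from the study, and "Subjects will need to contact the study PI".
- **Use of the reports (6.3 A and B).** "Reports of adverse events will be used to assess the safety of the study". A serious event that is life-threatening or fatal and "possibly, probably, or related to the research protocol, will trigger an immediate suspension of the research".

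On capacity, section 4.5 D states: "Given the nature of PWS, all patients will lack decision-making capacity and require surrogate consent". It then provides for an individual assessment by someone outside the study team, after which a subject found capable consents alone. Section 4.1 B admits patients with genetically confirmed PWS or with a documented code for hyperphagia.

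**The concern.** Guardians and surrogates take part in the screening call, the consent interview and the withdrawal of consent (1.3 A, 4.4, 4.5 D). They do not appear in the text on monitoring for adverse events, reporting them, receiving the stop instruction or notifying a hospitalisation. No staff-initiated question about adverse events is described at any point.

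The plan thus enrols some adults on another person's consent because they cannot decide for themselves, and then names those same adults as the only source of safety information during four weeks of daily home use. The PI's assessment, the DSMB review and the suspension rule all need a known event. An event that is not volunteered reaches none of them. In the results, missed events push in one direction, towards good tolerability. For the individual, a harm that is not reported cannot prompt the PI to review whether treatment should continue.

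**Working it through.** **Step 1. Who is named at each point.**

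| Function | Section | Named actor | Guardian or surrogate named? |
|---|---|---|---|
| Screening call, consent interview | 1.3 A, 4.4, 4.5 D | Participant with guardian or surrogate | Yes |
| Withdrawal of consent | 4.5 D | Subject or surrogate | Yes |
| Daily monitoring and report | 4.7 E | Participant | No |
| Side-effect diary | 1.7 A | Participant | No |
| Recipient of stop instruction | 4.7 E | Participant | No |
| Notice of hospitalisation | Hospitalization during study | Subject | No |

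**Step 2. Is there another route between Week 0 and Week 4?** Section 1.3 D lists weight at Weeks 1, 2 and 3, but describes no visit, call or adverse-event question to go with it. Sections 1.3 B and 1.9 A place the questionnaires, interviews and scans at Weeks 0 and 4. A surrogate's withdrawal of consent stops the supplement, but it does not report an event.

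**Step 3. How much under-reporting could matter.** The plan states no event rate and no reporting figure, so there is nothing of its own to reproduce. The inputs are:
- n = 10 (sections 1.5 and 4.3).
- The DSMB's in-study review after 30% of participants complete 14 days: 0.30 × 10 = 3 participants (section 6.3).
- p, the true proportion of participants with a reportable event: assumed.
- s, the chance that such an event is reported: assumed.

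Treat participants as independent, each with at most one reportable event. Then expected reports = n·p·s, and P(no report) = (1 − p·s)^n.

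For p = 0.30:

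| s | p·s | Expected reports in 10 | P(none in 3) | P(none in 10) |
|---|---|---|---|---|
| 1.0 | 0.30 | 3.0 | 0.70³ = 34% | 0.70¹⁰ = 3% |
| 0.7 | 0.21 | 2.1 | 0.79³ = 49% | 0.79¹⁰ = 9% |
| 0.5 | 0.15 | 1.5 | 0.85³ = 61% | 0.85¹⁰ = 20% |

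P(none in 10) over other assumed rates:

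| p | s = 1.0 | s = 0.7 | s = 0.5 |
|---|---|---|---|
| 0.1 | 35% | 48% | 60% |
| 0.2 | 11% | 22% | 35% |
| 0.5 | 0.1% | 1% | 6% |

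**Step 4. What a clean record would show.** With 0 of 10 events recorded, the one-sided 95% upper bound on the reported rate is 1 − 0.05^(1/10) = 26%. With full reporting, this is also the bound on the true rate. If half of events are reported, the bound on the true rate is 0.259 / 0.5 = 52%.

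**The case against.** Several objections have force.

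- **Capacity is not uniformly absent.** A reader might infer from the sentence in 4.5 D that no participant can report reliably. The same section allows self-consent after assessment, 4.1 B admits hyperphagia without PWS, and being unable to consent to research is not the same as being unable to mention bloating or constipation. This stands, and it limits the point to participants found to lack capacity.
- **Spontaneous report is not the only record.** A reader might infer that events are captured only when a participant speaks up. The diary is a second record, interim weights imply some contact, and staff see participants at Week 4. But the diary is participant-kept with no stated review date, and none of the contacts is described as including an adverse-event question.
- **Participant may be shorthand.** Section 4.4 C names only participants and the coordinator as signing the consent form, whereas 4.4 B also lists the surrogate and a witness. The safety text may be equally loose. That reading is possible, but a reporting duty should not depend on it.
- **Unseen appendices.** Appendix H (diary) and Appendix F (DSMB) are cited but were not available, and either could give the guardian a role. This stands as a limit.
- **The suspension rule.** A reader might infer that it cannot work, because the follow-up contact asks about severity and frequency while the rule turns on seriousness and relatedness. The physician's assessment in 4.7 E can supply both, so only an explicit statement is lacking.
- **Motive to conceal.** A reader might infer that food preoccupation gives participants a reason to hide symptoms and keep the muffins. No section says so, and the point does not need it.
- **Small numbers.** Even with full reporting and p = 0.30, the chance of no report in 3 participants is 34%. Much of the weakness at the DSMB review comes from n = 3, not from the reporting route.

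**Conclusion.** The point holds for participants enrolled by surrogate consent, on the text available. Followed as written, sections 1.7 A and 4.7 rest harm capture on people whom 4.5 D describes as lacking capacity, with no named guardian role and no staff-initiated query. The direction of bias is clear: missed reports make the product look better tolerated than it is.

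The size is not known. With an assumed 30% true rate, the chance of an empty record in 10 participants rises from 3% with full reporting to 9% at 70% and 20% at 50%. These figures depend on assumed rates, one reporting sensitivity for every kind of event, and independence between participants. That sensitivity should not be carried over to life-threatening or fatal events.

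The documents do not show that harms will in fact go unrecorded. They show an inconsistency between surrogate-based enrolment and participant-dependent safety reporting that should be removed before enrolment.

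**What to change.** In section 4.7 E and the paragraph on hospitalisation, for participants enrolled by surrogate consent:

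1. Name the guardian or caregiver as co-reporter of adverse events, including countersigning the diary and notifying the PI of a hospitalisation.
2. Have existing staff ask participant and guardian about adverse events at a fixed weekly contact, and review the diary then.
3. State that the PI's assessment records seriousness and relatedness in the terms used in section 6.3 B.

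Reconcile 4.5 D internally on capacity, and reconcile 4.7 E with 4.5 D on who receives the stop instruction. Check that Appendices F and H agree with the result. No stopping criterion is proposed or questioned here.

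The cost is protocol and diary wording plus about four short contacts per participant, at most 4 × 10 = 40 in all. Some proxy reports will be less exact than first-hand ones, and event counts may look slightly less favourable.
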